Day 64	[61, 67]
Day 71	[68, 74]
Day 78	[75, 81)

Day85	[82, 88]
Day92	[89, 95]
Day99	[96, 102]
Day 106	[103, 109]
Day 113	[110, 116]
Day 120	[117, 123]
Day 127	[124, 130]
Day 134	[131, 137]
Day 141	[138, 144]
Day 148	[145, 151]
Day 155	[152, 158)
Day 162	[159, 165]
Day 169	[166, 172]
Day 176 ---	[173, 182]
Day 190	[183, 196)
Day 204	[197, 210]
Day 218	[211, 224]
Day 232	[225, 238]
Day 246	[239, 252]
Day260	[253, 266]

Table 3 Visit window for Electrocardiogram

Analysis visit	Visit window
Baseline	last non-missing measurement prior to the first dose
Day29	[2, 53]
Day78	[54, 126]
Day 176	[127, 217] -
Day260	[218, 273]

Table 4 Visit window for Chemistry panel, Hematology, and Coagulation Panel

Analysis visit	Visit window
Baseline	last non-missing measurement prior to the first dose
Day5	(2, 8]
Day 12	(9, 13]
Day 15	[14, 18]
Day22	[19, 25)
Day29	[26, 32]
Day36	[33, 42]
Day 50	[43, 56]
Day64	[57, 70]
Day78	(71,84]
Day92	[85, 98]
Day 106	[99, 112]
Day 120	[113, 126]
Day 134	[127, 140]
Day 148	(141, 154]
Day 162	[155, 168]
Day 176	[169, 182]
Day 190	[183, 196]
Day 204	[197,210]
Day 218	[211, 224]
Day 232	[225, 238]
Day 246	[239, 252]
Day 260	[253, 266]

Table 5 Visit window for Blood Urea Nitrogen, Post-Dialysis BUN, Urea Reduction Ratio

Analysis visit	Visit window
----------------	--------------

Baseline	last non-missing measurement prior to the first dose
Day36	[2, 49]
Day64	[50, 77]
Day92	[78, 105]
Day 120	[106,133]
Day 148	(134, 161]
Day 176	[162, 189]
Day 204	[190, 217]
Day 232	[218,245]
Day260	[246, 273]

Table 6 Visit window for Inflammatory Markers

Analysis visit	Visit window
Baseline	last non-missing measurement prior to the first dose
Day 15	[2, 21]
Day29	[22, 39]
Day50	[40, 63]
Day78	[64, 91]
Day 106	[92, 119]
Day 134	[120, 147]
Day 162	[148, 168]
Day 176	[169, 189]
Day 204	[190,217]
Day 232	[218, 245]
Day 260	[246,273]

2.J.2 *Populations*

The following populations will be used in this study, and any exclusion of patients from the populations will be documented and decided upon by appropriate medical, clinical, data management, and statistical personnel at Ionis Pharmaceuticals prior to unblinding.

Intent-to-Treat Population (ITT)

All subjects randomized who have received at least 1 dose of Study Drug (ISIS 416858 or placebo). Results will be summarized under the treatment to which patients were randomized.

Per Protocol Population (PPS):

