All subjects who are randomized without missing more than 2 doses during the first 12 weeks or more than 5 doses over the 26-week Treatment Period and who do not have any major protocol violations that would affect the interpretation or integrity of the study results.

Safety Population:

All subjects randomized who have received at least 1 dose of Study Drug. Results for Cohorts A and B will be summarized under the treatment to which patients received.

Atrial Fibrillation (AF) Substudy population:

All randomized subjects who were reported at baseline as having a documented history of atrial fibrillation and have received at least 1 dose of Study Drug (ISIS 416858 or placebo).

PK Substudy Population:

All randomized subjects who participated in the PK subgroup and have received at least 1 dose of active Study Drug (ISIS 416858) and had at least 1 PK sample collected and analyzed with evaluable results for ISIS 416858 concentration.

PK Population:

All randomized subjects who have received at least 1 dose of active Study Drug (ISIS 416858) and had at least 1 PK sample collected and analyzed with evaluable results for ISIS 416858 concentration.

Platelet Function/Activation Substudy Population:

All subjects who participated in the Platelets Function/Activation substudy by having at least 1 evaluable sample assessed for flow cytometry and have received at least 1 dose of active Study Drug (ISIS 416858 or placebo).

In addition to the above analysis populations, it is recognized that some data displays will be provided for "All Screened" and "Screening Failures" patients.

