2.3 Safety Analyses

Safety analyses will be based on the safety population. Safety summary tables will be presented by treatment group and ISIS 416858 total.

2.3.1 *Exposure*

Treatment duration, time on study, number of doses and amount and total volume of Study Drug (ISIS 416858 or placebo) received will be summarized by treatment group and ISIS 416858 total.

The treatment duration (days) for each patient is defined as last dose date - first dose date +1.

The time on study will be defined as the total number of days a patient is known to be followed on study calculated as follows:

$$\text{Time on study} = \text{Last date on study} - \text{Date of first dose} + 1.$$

Where the last date on study is defined as the date of the latest visit with evaluation, or time of death from all available data for a given patient. Visits with refused or unable to contact are not visits with evaluation.

The amount of Study Drug received (mg) for each patient is defined as the total volume (mL) administered from the 200 mg/mL stock solution.

2.3.2 *Compliance*

Percentage of compliance will be calculated and summarized by treatment groups and ISIS 416858 total.

$$\text{Study drug compliance} = 100 \times (\text{Total number of doses with injections given} / \text{Total number of doses with injections expected}).$$

If a patient discontinued the study treatment, the total number of doses with injections expected is counted, per the schedule of injections, up to the last attended study visit during the treatment period.

2.3.3 *Adverse Events*

The treatment emergent adverse events (TEAE) are defined as those AEs that occurred after dosing and those existing pre-dose AEs that worsened post-dose during the study.

The most conservative approach will be used to determine if the event occurs during the treatment or follow-up periods:

- AEs that have onset dates or resolution dates prior to the first study treatment dates will be considered to have occurred prior to the study period. If the onset or resolution date

of an AE is a partial date with only month or year available or complete missing, then the event is assumed to be within the study period unless the year is prior to the year of the first study treatment date, or if in the same year, the month is prior to the month of the first study treatment date.

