2.4 Pharmacodynamic Analyses

The pharmacodynamic analysis will be conducted on the Per Protocol Population and will be presented according to treatment group and ISIS 416858 total. The baseline is defined as the latest- assessment prior to first dose of study drug.

Change and percent change from baseline FXI activity and antigen levels and aPTT will be summarized by treatment and visit separately. Individual results will be presented in data listings by treatment. Figures of the mean FXI activity and antigen levels and aPTT results as well as change and percent change from baseline will be provided by treatment group, and scheduled visit.

Change and percent change from baseline in FXI activity and antigen levels and aPTT will be compared between each of the ISJS-416858 treated group and pooled placebo group using the ANOVA or Wilcoxon Rank Sum test, as appropriate. The normality will be tested by applying Kolmogorov-Smirnov test on the residuals (difference between individual values and group mean). Numeric values will be rounded to 5 decimal places when applying Wilcoxon Rank Sum test or Kolmogorov-Smirnov test.

Frequency and percent of patients with average FXI activity .1, -2, s>.3, ..., :9.0U/mL during Day 50 to Day 176 (inclusive) up to last dose+ 7 days will also be provided.

The incidence and events for any aPTT>160s will be summarized by treatment and visit.

The clotting assessment will be conducted on the Per Protocol Population and will be presented according to treatment group and ISIS 416858 total.

The clotting assessment will consist of a quantitative scale by descriptive category (see details in table 1) and will be performed by trained personnel.

Table 1 Clotting Scale

Inspection site	Category 1	Category 2	Category 3	Category4
Air Trap	No clotting	Fibrinous ring with no clot formation on venous chamber filter	Clot formation on venous chamber	Coagulated system (treatment cannot continue without new setup)
Dialyzer	Clean dialyzer	Blood stripes affecting less than 5% of the fibers seen at the surface of the dialyzer	Blood stripes affecting 5% or more of the fibers seen at the surface of the dialyzer	Coagulated filter

Overall score is the highest of the individual component scores

Individual Category Summary

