1. STUDY INFORMATION

1.1. Protocol and Protocol Amendments

The protocol was amended 1 time. The latest versions of the protocol (Protocol Amendment 1) are provided along with the change summary for the revisions.

Protocol Version	Date	Document Provided
Original	01 June 2017	None
Protocol Amendment 1	14 June 2018	Protocol and change summary
Protocol Amendment 1 for Czech Republic	15 June 2018	Protocol and change summary
Protocol Amendment 1 for Austria	18 June 2018	Protocol and change summary

Notes to File	Date
Pregnancy Test will be Performed Once Every Month for Females of Childbearing Potential in Austria	31 July 2017
Protocol Clarification for Exclusion Criteria #2 and Day 2 Schedule of Procedures	18 December 2017
ISIS 416858-CSS - Blinded Safety Data Reviews	21 June 2018
ISIS 416858-CSS Randomization of Subject- with > 28-day Screening Period for Procedures	26 June 2018
Subject Data: Start Time and End Time of Dialysis Sessions	9 July 2018
ISIS 416858-CSS Protocol Clarification for Pregnancy Re-Testing	16 July 2018
ISIS 416858-CSS Protocol Clarification for Continuing on Study when Study Drug is Discontinued	1 August 2018
Dosing Error Subject- (Randomization-) at Site- (Rand-)	3 August 2018
ISIS 416858-CSS Clarification for Re-Testing of Subjects that have Platelets < 150,000/mm ³ During Screening	22 August 2018
ISIS 416858-CSS FXI Rainin Pipette Calibration Validation Periods	6 September 2018
ISIS 416858-CSS and Enrollment of MYTEMP Patients in Canada	10 September 2018
Unblinding of Lab Data for ISIS 416858-CSS Patient- (Rand-)	1 September 2018
Clarification of Aspirin and/or NSAID Use in Subjects in the Platelet Substudy	24 September 2018
ISIS 416858-CSS FXI Activity and Antigen Levels	19 October 2018
Immediate Change for Shipment Temperature of Hematology Samples (Sites [REDACTED])	28 December 2018
ISIS 416858-CSS Unblinded Local Lab Entity	4 March 2019

Notes to File	Date
Additional Medical Monitoring Requests in Study ISIS 416858-CSS	5 April 2019
ISIS 416858-CSS Per-Protocol Set (PPS)	7 June 2019
ISIS 416858-CSS Disallowed Concomitant Medication and Per-Protocol Set (PPS) Analysis	4 September 2019
ISIS 416858-CSS Study Dmg Intemption or Discontinuation Due to Low Platelets	4 September 2019
ISIS 416858-CSS Data Entry Errors: Date of Dosing	8 October 2019

IONIS PHARMACEUTICALS, INC.

ISIS 416858-CSS

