10.6 Planned Methods of Analysis

Descriptive summary analysis including mean, median, standard deviation, interquartile range (25th percentile, 75th percentile), and range (minimum, maximum) for continuous variables, and counts and percentages for categorical variables will be used to summarize most data.

Safety and PD assessments will be performed on the Safety population. Exploratory efficacy and clotting assessment measures may be assessed on the Per Protocol population.

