10.6.4 Pharmacodynamic Analysis

Pharmacodynamic analyses will be performed in the safety population. Change and percent change in FXI activity and antigen levels, aPTT, PT, and INR will be tabulated over time.

The extent and occurrence of clotting on the dialysis filters and circuit will be summarized descriptively by category scoring.

Table 5 Clotting Scale

Inspection Site	Category 1	Category 2	Category 3	Category 4
Air Trap	No clotting	Fibrinous ring with no clot formation on venous chamber filter	Clot formation on venous chamber	Coagulated system (treatment cannot continue without new setup)
Dialyzer	Clean dialyzer	Blood stripes affecting less than 5% of the fibers seen at the surface of the dialyzer	Blood stripes affecting 5% or more of the fibers seen at the surface of the dialyzer	Coagulated filter

Note: Overall score is the highest of the individual component scores

The relative occurrence of each clotting category will also be summarized from all obtained clotting assessments, whenever possible. Further details on the analysis of clotting assessments will be contained in the SAP.

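### The SAP moves the FXI and aPTT analyses, including the comparisons with placebo, to the Per Protocol Population, although the protocol assigns them to the Safety population

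*Combined protocol and SAP*

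**What the plan says.** SAP 2.4 opens with "The pharmacodynamic analysis will be conducted on the Per Protocol Population". Under that sentence come the change and percent change in FXI activity, FXI antigen and aPTT, their figures, the ANOVA or Wilcoxon comparisons of each active group with pooled placebo, and the table of aPTT values above 160 s. No second population is named for any of these.

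The protocol says otherwise in two places. Section 10.6: "Safety and PD assessments will be performed on the Safety population". Section 10.6.4: "Pharmacodynamic analyses will be performed in the safety population", followed by FXI activity, FXI antigen and aPTT by name. What Per Protocol may be used for is set out separately in 10.6: "Exploratory efficacy and clotting assessment measures may be assessed on the Per Protocol population".

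SAP 2.1.2 defines Per Protocol as randomized subjects "without missing more than 2 doses during the first 12 weeks or more than 5 doses over the 26-week Treatment Period" who also have no major violation affecting interpretation. Exclusions from the populations are settled by medical, clinical, data management and "statistical personnel at Ionis Pharmaceuticals prior to unblinding".

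**The concern.** Protocol 1.1 ties the primary objective to FXI activity reduction compared with placebo. An analysis set chosen by what happens after randomization does not preserve the randomized comparison for that measure. Study Drug can stop for low platelets, liver chemistry, bleeding or other reasons, and these need not occur equally in active and placebo groups. Deciding exclusions before unblinding stops anyone from choosing by arm, but it does not make the exclusions balanced.

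Two things are at stake. The late-visit FXI reduction in all dosed subjects may be overstated if excluded early stoppers are sampled off drug. And an aPTT above 160 s in an excluded subject would be missing from the SAP 2.4 incidence table, which carries safety information.

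The SAP offers no stated substitute. Apart from its definition, ITT is named only for baseline summaries (SAP 2.2). SAP 2.3.4 specifies visit summaries for chemistry and hematology, not coagulation. The SAP's list of modifications does not mention a change of PD population.

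**Working it through.** The core is the conflict between the texts set out above. The documents give no figure to reproduce, so the arithmetic below shows only who is removed and how far an estimate could move.

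**Who is removed.** Dose k falls on Day 1 + 7(k − 1), so dose 20 is Day 134, dose 21 is Day 141 and dose 26 is Day 176. The definition does not say whether doses not given after discontinuation are missed doses. If they are, a subject whose last dose is number k is excluded when 26 − k > 5 or 12 − min(k, 12) > 2, that is, when k ≤ 20. A stop after doses 21 to 25 leaves 5 to 1 missed and the subject may stay in.

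**What is lost.** SAP Table 4 has 16 treatment-period coagulation windows: Days 5, 12, 15, 22, 29, 36, 50, 64, 78, 92, 106, 120, 134, 148, 162 and 176. Thirteen are at or before Day 134, so a subject stopping at dose 20 loses on-drug values in up to 13 of the 16.

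**Overstatement at Day 176.** Inputs:
- E, the on-drug FXI reduction: 80%, the expected maximum in protocol 2.4; or 62%, from 0.38 U/mL at 200 mg in the earlier knee-arthroplasty study, assuming a baseline of 1.0 U/mL.
- q, the share of the arm excluded: 10/20/30% (assumed).
- s, the share of the excluded who are off-drug stoppers, the rest being on drug (assumed).
- m, the share of stoppers measured (assumed).
- r, their fractional recovery toward baseline (assumed).

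Overstatement = E·q·s·m·r / (1 − q·s + q·s·m), in percentage points:

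| Scenario | q = 10% | 20% | 30% |
|---|---|---|---|
| E = 80, s = m = r = 1 (ceiling) | 8 | 16 | 24 |
| E = 62, s = m = r = 1 | 6.2 | 12.4 | 18.6 |
| E = 80, r = 0.5 | 4 | 8 | 12 |
| E = 80, m = 0.5 | 4.2 | 8.9 | 14.1 |
| E = 80, s = 0.5 | 4 | 8 | 12 |
| E = 80, s = m = r = 0.5 | 1.0 | 2.1 | 3.2 |
| m = 0, or on-treatment values only | 0 | 0 | 0 |

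Example, m = 0.5 and q = 20%: 80 × 0.2 × 0.5 / (1 − 0.2 + 0.1) = 8 / 0.9 = 8.9.

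**How much effect a stopper would keep.** Protocol 5.1 equates 84 days with about 5 half-lives, so one is 84 / 5 = 16.8 days. Assume the FXI effect fades at that rate. The Day 176 sample is taken before dialysis and dosing follows dialysis, so the on-drug comparator is 7 days after the Day 169 dose. A Day 134 stopper keeps 2^(−(42 − 7)/16.8) = 0.236 of that trough effect. A Day 141 stopper keeps 2^(−(35 − 7)/16.8) = 0.315.

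**Effect on the test.** Planned sizes are 68 × 0.75 = 51 per active dose and 3 × 17 = 51 pooled placebo. Assume SDs of 20 (active) and 25 (placebo) points and no mean change on placebo.
- No dilution: t = 80 / √((400 + 625)/51) = 17.8.
- Ceiling at q = 30%: mean 56, variance 400 + 0.3 × 0.7 × 80² = 1744, t = 56 / √((1744 + 625)/51) = 8.2.

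The estimate moves; the test result does not.

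**The case against.** The strongest reply has four parts.

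1. *Per Protocol suits a pharmacodynamic question, and an all-dosed summary may exist anyway.* Protocol 10.6.2 commits to summarizing the coagulation panel by visit and group as a safety laboratory, Appendix B puts FXI and aPTT in that panel, and SAP 1.3.1 and Table 4 also treat coagulation as a safety evaluation. This stands in part: a descriptive Safety-population table may be implied. It does not supply the comparisons with placebo, which appear only in SAP 2.4. Per Protocol can remain as a supportive analysis.

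2. *The numbers measure a choice about off-drug data, not the population conflict.* Every non-zero entry needs off-drug values to enter the late visits, and the protocol does not require that they do. This is fair, and the table is only an illustration. The direction is not fixed either: stops for low platelets or bleeding could remove strong responders, and at early visits and for aPTT the sign is uncertain.

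3. *The dose-20 cut-off rests on an unstated rule.* It does. SAP 2.3.2 counts expected doses for compliance only "up to the last attended study visit during the treatment period", and the contents of two 2019 notes to file on the Per-Protocol Set are not shown. Major violations are a separate route to exclusion.

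4. *Importance is limited.* The only outcome labelled primary is major plus clinically relevant non-major bleeding, and the synopsis objective does not mention FXI. But SAP 1.2.1 and protocol 1.1 do name FXI reduction in the primary objective.

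None of this explains why the SAP departs from the protocol's stated population.

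**Conclusion.** The concern holds and should be fixed. The conflict is explicit in current text, no reason for it is shown, and it affects a measure named in the primary objective. Clotting is not part of the problem, since the protocol permits Per Protocol there.

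Confidence is high on the conflict and on the selection it introduces, and much lower on the size and direction of any bias. The illustrated range of 0 to 24 points depends on assumed exclusion, stopping, sampling and recovery rates and on an expected maximum effect. Significance against placebo is little affected, and the bleeding outcome is not affected.

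**What to change.** In SAP 2.4:
- Make the Safety population the main set for FXI activity, FXI antigen and aPTT, including the table of aPTT above 160 s, as protocol 10.6 and 10.6.4 state. Keep Per Protocol as supportive, and leave clotting where it is.
- State that between-group comparisons are by randomized treatment. The ITT set has the same members, whereas the as-treated sentence in the Safety definition names only Cohorts A and B.
- Use all collected values, show the number measured at each visit, and present an on-treatment version beside them, using the window of last dose + 7 days that SAP 2.4 already applies elsewhere. Including off-drug values is a recommendation, not a protocol requirement.

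In SAP 2.1.2, state whether doses not given after discontinuation count as missed.

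The cost is SAP wording and one more set of FXI and aPTT tables, with a possibly less favourable late-visit FXI reduction.

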1.4 Randomization & Treatment Allocation

Subjects will be randomized on Study Day 1 after all screening assessments have been completed and after the Investigator has verified that they are eligible. No subject may begin treatment prior to randomization and assignment of a unique subject identification number.

All subjects will be randomized using an automated system (IXRS). Subjects will be stratified based on the diagnosis of documented atrial fibrillation (AF) at Screening (Yes/No), enrolled in PK substudy (Yes/No), enrolled in Platelet substudy (Yes/No), and then subjects will be randomized to 1 of 3 dose cohorts in a 1:1:1 ratio (Cohort A, Cohort B, and Cohort C). Within each dose cohort, subjects will be randomized in a 3:1 ratio to receive treatment with Study Drug (either ISIS 416858 or placebo).

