2.6 Other Study Outcomes and Evaluations

Blood Urea Nitrogen (BUN) will be used for Urea Reduction Ratio (URR) analysis in the Safety population.

$$\text{URR} = (\text{Upre} - \text{Upost}) / \text{Upre} \times 100\%$$

where U_{pre} is the pre-dialysis blood urea nitrogen (BUN) level in serum and U_{pos1} is the post-dialysis blood urea nitrogen (BUN) level in serum. The URR generated from Lab will be used.

URR and sp Kt/v values as well as the change and percent change from baseline will be summarized for each visit by treatment group for the safety population. Single pool dialyzer clearance of urea (sp Kt/v) from CRF will be used in the summary.

Change and percent change from baseline will be compared between each of the ISIS 416858-treated groups and the pooled placebo group using the ANOVA or Wilcoxon Rank Sum test, as appropriate. The normality will be tested by applying Kolmogorov-Smirnov test on the residuals (difference between individual values and group mean).

Changes in dialysis prescription will be listed.

2.6.J Platelet Function tests

All Flow cytometry and PFA results will be summarized by visit and treatment for Platelet Function/Activation Substudy population.

Flow cytometry results (and potentially a report with interpretation of the results) will be provided directly by Boston Children's hospital. Flow cytometry results of platelet-monocyte and platelet-neutrophil aggregates and platelet surface P-selectin and platelet surface activated GPIIb-IIa will be compared between each of the ISIS 416858-treated groups and the pooled placebo group.

The PFA results of duplicate closure times for each evaluated cartridges of collagen/EPI, collagen/ADP, and INNOVANCE PFA®P2Y (optional cartridge) for change and percent change from baseline will be compared between each of the ISIS 416858-treated groups and the pooled placebo group for subjects that have the PFA tests performed.

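### FXI, aPTT, URR and sp Kt/V are compared with pooled placebo without a baseline covariate or a prespecified between-group difference and CI, and the rule for choosing the test is incomplete (minor)

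*Combined protocol and SAP*

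**What the plan says.** For FXI activity, FXI antigen and aPTT, SAP 2.4 compares change and percent change between each dose and the "pooled placebo group using the ANOVA or Wilcoxon Rank Sum test, as appropriate". The next sentence gives the criterion: "The normality will be tested by applying Kolmogorov-Smirnov test on the residuals", with a residual defined as an individual value minus its group mean. SAP 2.6 repeats the scheme for URR and sp Kt/V: "Change and percent change from baseline will be compared between each of the ISIS 416858-treated groups and the pooled placebo group", again by ANOVA or Wilcoxon with the same normality check. SAP 2.1.1 sets a two-sided 5% level for all tests unless stated otherwise.

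Neither section names a covariate or asks for an estimated difference or interval. By-arm summaries are planned: "Change and percent change from baseline FXI activity and antigen levels and aPTT will be summarized by treatment and visit separately" in 2.4, and "URR and sp Kt/v values as well as the change and percent change from baseline will be summarized for each visit by treatment group" in 2.6. Protocol 10.6.4 plans tabulation only.

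The clotting part of SAP 2.4 goes further. It adds models with baseline clotting category as covariate and asks for odds ratios, p-values and 95% CIs.

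The analysis population matters for the group sizes below. SAP 2.4 states "The pharmacodynamic analysis will be conducted on the Per Protocol Population", while Protocol 10.6.4 states "Pharmacodynamic analyses will be performed in the safety population". SAP 2.6 uses the safety population.

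**The concern.** FXI activity is the measure named in the primary objective, and URR and sp Kt/V are the dialysis adequacy measures. With three doses and no statistical rationale for the sample size, the useful output is an estimate with an interval for each dose, more than a p-value against placebo. The plan prespecifies only the p-value, and if Wilcoxon is selected no effect measure is named at all.

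Baseline enters only by subtraction or division. When baseline and follow-up are imperfectly correlated, a change score usually carries more noise than a baseline-adjusted comparison. The test-choice step also leaves room for two programmers to follow the SAP and report different tests.

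**Working it through.** **Group sizes.** 204/3 = 68 per cohort. At 3:1 this gives 51 active and 17 placebo; pooled placebo is 3 × 17 = 51. Each comparison is 51 vs 51 as randomized. Retention in the Per Protocol Population is not given, so 31 to 51 per group is used as an assumed range for FXI and aPTT. The documents state no power, SD or correlation, so there is no plan figure to reproduce, and every SD and correlation (rho) below is assumed.

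**1. URR and sp Kt/V (equal SDs).** In SD² units, the variance of a group difference is (2/n) × 2(1 − rho) for change scores and (2/n) × (1 − rho²) for ANCOVA. The ratio is (1 + rho)/2. Half-width of the 95% CI at n = 51, as 1.96 × square root:

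| rho | ratio | change score (SD) | ANCOVA (SD) |
|---|---|---|---|
| 0.3 | 0.65 | 0.46 | 0.37 |
| 0.5 | 0.75 | 0.39 | 0.34 |
| 0.7 | 0.85 | 0.30 | 0.28 |
| 0.9 | 0.95 | 0.174 | 0.169 |

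**2. FXI activity change.** Assumed: baseline and placebo follow-up SD 0.25, treated follow-up SD 0.10, means 1.0 and 0.3 U/mL, rho 0.3 or 0.6 on treatment and 0.5 or 0.9 on placebo. One case in full (0.3 and 0.5):
- Change scores: treated 0.25² + 0.10² − 2(0.3)(0.25)(0.10) = 0.0575; placebo 2(0.25²)(1 − 0.5) = 0.0625; sum 0.1200. SE = √(0.1200/51) = 0.0485.
- Pairwise ANCOVA: common slope (0.3 × 0.10/0.25 + 0.5)/2 = 0.31. Residual variances are 0.0114 and 0.0491; sum 0.0605. SE = √(0.0605/51) = 0.0344.
- Ratio 0.0605/0.1200 = 0.50.

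Simulation over all four correlation pairs and 31 to 51 per group gives ratios of 0.50 to 0.60. Half-widths fall from 0.065–0.094 to 0.050–0.068 U/mL at 51 per group, and from 0.083–0.122 to 0.064–0.087 at 31. Over a wider SD grid the ratio is 0.46 to 0.89; for percent change it is 0.78 to 0.96. The unadjusted z is 11 to 21 throughout, so detection of the FXI effect does not depend on the model.

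**3. aPTT.** With treated follow-up SD 1.5 to 2 times baseline, the simulated ratio is 0.80 to 1.015. There may be no gain.

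**4. One four-arm ANCOVA for FXI.** A common error variance averages three low-variance treated arms with one higher-variance placebo arm. In the same case the four-arm slope is (3 × 0.12 + 0.5)/4 = 0.215, and the residual variances are 0.00966 and 0.05195. The true variance of a dose-placebo difference is proportional to 0.00966 + 0.05195 = 0.0616. The model uses 2 × (3 × 0.00966 + 0.05195)/4 = 0.0405. The SE is understated by √(0.0405/0.0616) = 0.81, so a nominal 95% interval covers about 89%. Simulation over the four pairs gives about 88% to 92%, against about 95% for pairwise fits or robust variances.

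**5. Test choice.** With four groups of 51, the rate at which normality is rejected depends on the critical values:

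| data | standard | allowing for estimated parameters |
|---|---|---|
| normal | 0.0% | 5.4% |
| t, 4 df | 21.7% | 76.1% |
| lognormal 0.5 | 88.3% | 99.9% |

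At a 0.5 SD effect, ANOVA and Wilcoxon disagree at 5% in 7.2%, 12.8% and 15.6% of runs. Type I error of the two-stage procedure was 4.4% to 5.7% across all settings run. If the check is made per visit and also uses estimated-parameter critical values, normal data still give a mixture of tests with probability 0.42 to 0.58 over the 16 on-treatment coagulation windows (SAP Table 4) and 0.22 to 0.28 over the 6 URR windows (SAP Table 5). With standard critical values, the figure for the 16 windows is close to zero.

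**6. AF term.** With an assumed 15% AF prevalence and an AF effect of 0 or 0.3 SD, adding AF changes the variance by a factor of 1.00 to 1.014.

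**The case against.** The strongest reply is that a change-score comparison is valid in a randomized trial, that by-arm summaries by visit let anyone derive an unadjusted difference, and that preferring ANCOVA is partly taste. All of that stands, and it keeps the point minor. It does not answer why clotting receives a baseline covariate, an estimate and an interval while the measure in the primary objective does not.

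A reader might infer that the SAP has no rule for choosing the test. The documents do not support that: the Kolmogorov-Smirnov sentence is a criterion, and SAP 2.1.1 supplies its default level. What is missing is which result leads to which test, whether the check is run per endpoint, dose or visit, and which critical values apply.

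A reader might also infer that leaving the AF stratum out costs precision. On the assumed inputs it does not; the only argument for the term is consistency with the stratified randomization.

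Finally, the absence of covariates is inferred from none being listed and from residuals being taken about the group mean. The SAP does not describe the model as treatment-only.

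**Conclusion.** The point holds as a minor one. For FXI activity, FXI antigen, aPTT, URR and sp Kt/V, the plan gives up precision and does not commit to one comparable effect estimate per dose; its test-selection wording is incomplete. The gain from adjustment ranges from substantial (FXI change, or URR and sp Kt/V at low rho) to negligible (rho 0.9, or aPTT).

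It would be wrong to conclude that the p-values are invalid, that type I error is inflated, or that an FXI effect could be missed. The primary safety outcome, major plus clinically relevant non-major bleeding, is untouched. The sizes rest wholly on assumed SDs, correlations and retention; the absence of a covariate, a difference and an interval rests on the text.

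**What to change.** For each endpoint, prespecify ANCOVA, or a repeated-measures model, with treatment and baseline value. Report each dose's adjusted difference from pooled placebo with a 95% CI.

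For FXI activity, FXI antigen and aPTT, require either a separate fit for each dose-placebo pair or heteroscedasticity-robust variances. This should not be optional, because a single common-variance four-arm model gives FXI intervals that are too narrow.

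Drop the normality check as the selector and give Wilcoxon as a sensitivity analysis for every comparison. The AF stratum may be included for consistency with the randomization, with no precision gain claimed.

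The cost is SAP text and programming. Baseline values and AF status are already collected; subjects, visits and sample size do not change.
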